3. Medical history includes demographic information and medical and surgical history. Cancer history includes current cancer diagnosis, treatment regimens (regimen, doses, start and stop dates), and best response for each regimen.
4. A complete physical exam is required at the Screening and the Post-Treatment Safety Assessment visits. Otherwise, a symptom-directed physical exam should be performed where indicated.
5. ECOG (Eastern Cooperative Oncology Group) performance status ([Appendix 1](#)).
6. Vital signs include blood pressure, pulse, temperature, and respirations. On Day 1 of each cycle, vital signs will be recorded prior to INXN-1001 dosing and hourly for the first two hours after INXN-2001 dosing. Blood pressure is to be monitored closely to prevent hypotension after administration of INXN-1001. Blood pressure assessment is required on Day 3 or Day 4 for Cycle 1 and Cycle 2. Subjects must be instructed to maintain adequate oral hydration on and in between dosing days; sites must closely monitor subjects' hydration status.
7. Monitoring and recording of adverse events (AEs) and serious adverse events (SAEs) will be conducted throughout the study. AEs/SAEs that occur following informed consent until the Post-Treatment Safety Assessment must be recorded on the AE CRF. In addition, all SAEs must be reported by the investigator or designee within 24 hours of becoming aware of the event, from the time of informed consent through 30 days after the last dose of study drug, regardless of the initiation of any new anti-cancer therapy.

8. Concomitant medication information, including blood products, vitamins and other supplements will be collected for the time period beginning 28 days prior to the first dose of study drug, through the Follow-Up Tumor Assessment visit.
9. Females of childbearing potential will have a serum pregnancy test at the Screening visit and a urine pregnancy test on the first day of each treatment cycle, prior to administration of INXN-1001.
10. Hematology tests include: complete blood count and white blood cell count, differential white blood cell count, red blood cell count, hematocrit, hemoglobin, red blood cell indices, reticulocyte count, MCV (mean corpuscular volume) and platelet count. PTT (partial thromboplastin time) and INR (international normalized ratio) will also be evaluated.

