1-2 hours post INXN-1001 dosing
3-6 hours post INXN-1001 dosing

Day 2: Pre-dose (< 30 minutes prior to INXN-1001 dosing)

Day 13: 1-2 hours post INXN-1001 dosing
3-6 hours post INXN-1001 dosing

Day 15: Anytime >24 hours post-Day 13 INXN-1001 dose

27. Blood pressure will be assessed at Cycle 1 and Cycle 2 Day 3 or 4 visit. During Cycle 1 and 2, Day 3 or 4 visits are required. For Cycles 3-6, Day 3 or 4 visits should be performed when feasible (eg, Monday through Friday).

28. Post-Treatment Safety Assessment visit will be performed 28 ± 3 days after the last dose of INXN-1001 or at the time of early withdrawal from study treatment.

29. A Follow-Up Tumor Assessment visit will be performed 35 ± 7 days after the Post-Treatment Safety Assessment visit. This assessment is required for all subjects, including those with prior objective evidence of disease progression to ensure that more slowly declining tumor burden in response to therapy is not missed.

Subjects without objective evidence of disease progression should continue to have tumor assessments performed at 8 -10 weeks intervals until irPD has been confirmed or an alternate anti-cancer therapy has been initiated, whichever occurs first.

30. Interim cancer history information will include documentation of any new concomitant medications and any anti-cancer treatments received since the Post-Treatment Safety Assessment visit or previous tumor assessment.

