9.3 DOCUMENTING ADVERSE EVENTS (AES)

All AEs (including SAEs) are to be accurately recorded on the Adverse Event page of the patient's eCRF from the time the patient signs the informed consent until the post-treatment safety visit. Each event will be assessed for serious criteria, severity, and causality (See "Causality Assessments"). The date of onset, as well as the duration of the event will be recorded. In addition, treatments provided to the patient, actions taken with the study drugs, and the outcome of the AE will also be noted.

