9.4 REPORTING SERIOUS ADVERSE EVENTS (SAEs)

Time Frame for Reporting

SAEs must be reported to the Sponsor or Sponsor's designee within 24 hours of becoming aware of the event (regardless of the initiation of any new anti-cancer therapy) including the following:

- Any death or SAE experienced by the patient from the signing of informed consent to 30 days after the last dose of study drug, regardless of relationship to study drug.
- Any death or SAE that the Investigator becomes aware of, and believes to be study drug related, that occurs more than 30 days after the patient last received study drug.

Study drug-related AEs/SAEs that are ongoing at the time of the Post-Treatment Safety Assessment visit should continue to be followed until resolution, return to baseline, or until they have stabilized or become chronic (and following consultation and agreement by the ZIOPHARM Medical Monitor).

Information to be provided by the Investigator

Within 24 hours of becoming aware of the SAE or patient death, the Investigator must notify the Sponsor or designee and transmit information to the Sponsor or designee. Information (initial and follow-up) should be provided on an electronic and/or paper SAE Report form signed and dated by the Investigator. The SAE Report form and copies of source documents (with patient identifiers redacted) will be transmitted electronically or by fax. A hospital discharge summary should be provided if the subject was hospitalized. An SAE report will be considered final once all relevant information has been received and reviewed by the Sponsor.

The SAE Report form is provided in the Investigator study files. Please refer to the Investigator study files for instructions on how to complete the form. The Investigator will provide all of the following information related to the event:

- Investigator identification
- Patient identification (eg, patient number, initials, sex, age or date of birth)
- Information regarding study drug administration (eg, start/stop date, dose and frequency)
- Description of event
- Action taken with the study drugs in relation to the SAE
- Outcome of the SAE

In addition to the above information, the Investigator must provide, for each event term, an assessment of:

- Severity/intensity
- Relationship to the study drug (causality assessment)

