10.3.2 Safety Analyses

The Safety Population will be used for the analyses of safety data based on the dose of INXN-1001 received.

Safety evaluations will be based on the incidence, intensity, and type of AEs and SAEs. Clinically significant changes in the subjects' physical examinations, vital signs, and ECG evaluations, and clinical manifestations relevant to abnormal laboratory values will be captured as AEs. Safety will also be assessed based on medical history and prior/concomitant medications.

AEs will be coded using the Medical Dictionary for Regulatory Activities (MedDRA[®]) for the purpose of summarization. All AEs occurring during the study will be included in by-subject data listings. Treatment-emergent events will be tabulated. 'Treatment-emergent' is defined as any AE that occurs during or after administration of the first dose of study drug through the Post-Treatment Safety Assessment visit (28 days after the last INXN-1001 dose); any event after the first dose of study drug that is considered study drug-related regardless of the start date of the event; or any event that is present at baseline that worsens in intensity or is subsequently considered to be drug related by the investigator. Deaths, SAEs, and AEs resulting in study discontinuation will be listed.

Safety variables will be tabulated and presented by dose cohort. Exposure to study drug and reasons for discontinuation of study treatment will be tabulated.

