12.2 Adverse Events

Adverse events will be coded according to MedDRA dictionary version 10.

Symptoms and signs of exacerbation or worsening of the patient's primary disease will be captured as AEs.

A treatment emergent adverse event (TEAE) is defined as an AE occurring during or after administration of first dose of study drug, or any event after the first dose of study drug considered study drug-related regardless of event start date, or any worsening in intensity or event considered drug related by the investigator of a pre-existing medical condition/AE with onset after the start of study drug, and until Post-Treatment Safety Assessment visit (28 days after the last INXN-1001 dose per patient). AEs with unknown start date/time will be assumed to be treatment-emergent

unless the end date/time is known to be before start of study drug. AEs with onset after the completion of screening but prior to the start of study drug will be considered non-treatment emergent.

An overall AE summary will be presented for all AEs and the pre-defined subsets of events below:

- Any AEs
- Any TEAE events
- Any drug-related AEs
- Any CTC Grade 3 or greater AEs
- Any CTC Grade 3 or greater drug-related AEs
- Any AEs leading to death
- Any drug-related AEs leading to death
- Any serious AEs (SAEs)
- Any drug-related serious AEs
- Any AEs leading to discontinuation
- Any drug-related AEs leading to discontinuation
- Any dose limiting toxicities

Related is defined as 'possibly related' or 'related' to treatment in the opinion of the investigator.

Both number of events and number of patients will be tabulated. For patients, percentages will be calculated from the total number of patients per INXN-1001 dose cohort in each phase and group (for phase II only).

Summaries of TEAEs, drug-related adverse events, SAEs, drug-related SAEs, AEs with CTC grade ≥ 3 , drug-related AEs with CTC grade ≥ 3 and AEs leading to discontinuation will be tabulated by MedDRA System Organ Class (SOC) and specific AE preferred Term (PT) sorted by decreasing frequency within SOC. Both number of events and number of patients will be tabulated. For patients, percentages will be calculated from the total number of patients per INXN-1001 dose group.

All AEs, TEAEs, SAEs, drug-related adverse events, adverse events leading to discontinuation of study medication and adverse events leading to death will be listed.

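### Early-withdrawal safety visits can end AE recording before the 28 days after last dose that the treatment-emergent definition assumes, so new non-serious AEs in that gap need not be captured

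*Protocol*

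**What the plan says.** **Timing of the visit.** Protocol Table 2, footnote 28, places the PTSA 28 ± 3 days "after the last dose of INXN-1001 or at the time of early withdrawal from study treatment". Section 8.4.4 repeats the early-withdrawal alternative. Appendix 5 refers back to the Table 2 footnotes, so it also applies to Phase I and Phase II Group 1. Section 7.3 asks subjects who stop study drug to complete the visit but gives no interval. The synopsis (Duration of Subject Participation), Section 11.4 and the duration entry in Appendix 5 give 28 days and no alternative.

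**End of AE recording.** Footnote 7 states: "AEs/SAEs that occur following informed consent until the Post-Treatment Safety Assessment must be recorded on the AE CRF". Section 8.4.2.6 says the same, and Section 9.3 has AEs recorded on the eCRF "from the time the patient signs the informed consent until the post-treatment safety visit". None of these sets a minimum number of days after the last dose.

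**Analysis window.** Protocol 10.3.2 counts events as treatment-emergent "through the Post-Treatment Safety Assessment visit (28 days after the last INXN-1001 dose". SAP 12.2 counts them "until Post-Treatment Safety Assessment visit (28 days after the last INXN-1001 dose per patient".

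**Other cover.** Section 9.4 requires reporting of "Any death or SAE experienced by the patient from the signing of informed consent to 30 days after the last dose of study drug", and of later deaths or SAEs believed to be drug-related. Sections 9.4 and 9.6 require follow-up of related events still ongoing at the PTSA. Protocol 10.3.2 also counts as treatment-emergent "any event after the first dose of study drug that is considered study drug-related regardless of the start date of the event".

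**The concern.** The analysis sections treat the visit and day 28 as the same moment. They coincide, within ± 3 days, only for a subject seen on schedule. When the PTSA is held at early withdrawal, the duty to record AEs ends with it, and the treatment-emergent period is then either shorter than 28 days or partly unobserved.

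Safety and tolerability are the primary objective (Protocol 6.1, SAP 3.1). Early withdrawal is also not a random event here: Sections 6.2.4, 7.3 and 8.2.6 make it mandatory or the default for DLTs and related Grade 3 or 4 events. Cohorts are small. SAP 1.0 gives 2 to 4 patients per regimen, so one preferred term missed in one patient changes that term's cohort percentage by 25 points (1/4) to 50 points (1/2).

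**Working it through.** No sample-size or power figure is involved; the check is a day count.

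**Inputs from the documents**
- Scheduled PTSA (footnote 28): 28 − 3 = 25 to 28 + 3 = 31 days after the last INXN-1001 dose.
- Group 2 dosing (footnote 24, Section 8.2.3): 7 doses, every other day, on Days 1, 3, 5, 7, 9, 11 and 13 of a 28-day cycle.
- Phase I and Group 1 dosing (Section 8.2.3): Days 1 to 7 of a 21-day cycle.
- Treatment delays allowed at weekly steps, up to 4 weeks (Section 8.2.6).

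**Assumption.** The documents do not say when early-withdrawal visits took place. The days below are illustrations spanning the possible range. At the next Day 1, withdrawal is taken to occur before dosing.

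**Formulas**
- Days recorded after last dose = PTSA day − last dose day.
- Shortfall = max(0, 28 − days recorded).

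| PTSA held at | Group 2: recorded; shortfall | Phase I and Group 1: recorded; shortfall |
|---|---|---|
| A dosing day | 0; 28 | 0; 28 |
| Cycle Day 15 | 15 − 13 = 2; 26 | 15 − 7 = 8; 20 |
| Next Day 1 | 29 − 13 = 16; 12 | 22 − 7 = 15; 13 |
| Next Day 1 + 1 week | 36 − 13 = 23; 5 | 29 − 7 = 22; 6 |
| Next Day 1 + 2 weeks | 43 − 13 = 30; 0 | 36 − 7 = 29; 0 |

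The shortfall therefore runs from 0 to 28 days. Measured against the 25-day lower limit of the scheduled window, a one-week delay still leaves 25 − 23 = 2 days (Group 2) or 25 − 22 = 3 days (Phase I and Group 1).

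**What falls in the gap.** Taking event types in turn for an onset after an early PTSA and within 28 days of the last dose:
- Death or SAE: reported under Section 9.4, though the AE CRF duty in footnote 7 has already ended.
- Related AE already ongoing at the visit: followed under Sections 9.4 and 9.6.
- New non-serious AE, related or not, including a non-serious Grade 3 or laboratory event: no section requires it to be recorded.

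**Is a later visit available?** Footnote 29 requires the Follow-Up Tumor Assessment for all subjects 35 ± 7 days after the PTSA, so 28 to 42 days after it. Even with the PTSA on the day of the last dose, this visit falls at least 0 + 28 = 28 days after that dose. Footnote 8 collects concomitant medication through it; the AE row of Table 2 does not extend to it.

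**The case against.** The case on the other side has real force.

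- **Headline rates.** A reader might infer that treatment-emergent incidence is pushed down most where tolerability is worst. The documents do not support that for the patient-level summary. Under SAP 12.2 a subject withdrawn for a DLT or a related Grade 3 or 4 event already counts in the rows for any TEAE, drug-related AEs, Grade 3 or greater, AEs leading to discontinuation and, where it applies, DLTs. A shorter tail cannot remove that subject. The MTD rests on Cycle 1 DLTs (Section 6.2.5), and a subject withdrawn for one is already counted.
- **Size.** A reader might assume a visit 3 to 7 days after the last dose and conclude that 75% to 89% of follow-up is lost ((28 − 7)/28 and (28 − 3)/28). No section supports that interval. A subject found at the next Day 1 not to meet the retreatment criteria loses 12 to 13 days, and a two-week delay closes the gap.
- **Safeguards.** Serious and ongoing related events are covered as described, and footnote 7 also speaks of AE monitoring and recording throughout the study. A reading in which all safety capture stops at the PTSA is therefore too strong.
- **Existing contact.** The 30-day SAE rule might suggest that a contact at that time already exists. Section 9.4 sets a reporting duty; Table 2 schedules no such contact.

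All four points stand as limits. They do not close the gap. The general sentence in footnote 7 is followed by the specific one that ends CRF recording at the PTSA. The relatedness clause in Protocol 10.3.2 cannot count an event that nobody had to record, and in SAP 12.2 the closing time limit can be read as applying to related events too.

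**Conclusion.** The inconsistency is real and should be corrected. Footnote 28 and Section 8.4.4 cannot be squared with the 28-day description in Protocol 10.3.2 and SAP 12.2, or with the synopsis, Section 11.4 and Appendix 5. Following the plan as written leaves new-onset non-serious AEs between an early PTSA and day 28 outside required recording.

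The shortfall per affected subject is 0 to 28 days, depending on an assumed withdrawal day. The number of subjects with an early PTSA is not stated, so the effect on AE tables cannot be computed. For subjects withdrawn for a DLT or a Grade 3/4 event, the loss is in later preferred terms and event counts, not in the patient-level summary rows. The study is descriptive (SAP 9.0 plans no inferential statistics), so the damage is to completeness of the safety description in subjects who stop early, not to a test or to DLT counting.

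**What to change.** **Protocol.** Reconcile footnotes 7 and 28 and Sections 8.4.4, 8.4.2.6 and 9.3 with the 28-day definition. State that all AEs are recorded through 28 (±3) days after the last INXN-1001 dose for every treated subject, whenever the PTSA takes place. For a subject with an early PTSA, collect the remaining period by an AE query at the Follow-Up Tumor Assessment already required, or by one telephone contact.

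**SAP 12.2.** Define the treatment-emergent window by days since the last INXN-1001 dose, not by visit date. List each subject's last-dose-to-PTSA interval and flag intervals under 25 days as incomplete AE follow-up. This matters because SAP 1.0 and 6.1 describe the 26 patients (13 + 13) as already treated: redefining the window cannot recover events that were never recorded, but the flag tells the reader where follow-up was short.

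**Cost.** One added AE query per early withdrawal, some protocol wording and one listing. TEAE counts may become slightly less favourable. A query captures events the subject or site knows of; it does not add laboratory tests after the PTSA.

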5. INTRODUCTION

5.1 DISEASE BACKGROUND (MELANOMA)

The incidence of melanoma has been increasing steadily in the U.S. and other developed countries for decades. At present, the incidence rate among the U.S. population is roughly 1 in 60. Solar radiation exposure is an important risk factor, but genetic risk factors multiply this, and a family history of melanoma is a strong indicator of risk.

Current treatment of melanoma involves surgical resection, which is highly effective when the melanoma is identified early. Systemic chemotherapy with a number of standard anti-neoplastic agents may have transient palliative success for more advanced disease that is beyond surgical cure, but there is no evidence of any significant prolongation of survival with any systemic currently available agents.² Immunotherapy approaches have been employed with evidence of significant benefit and include the use of interferon (IFN) alpha-2b, interleukin-2 (IL-2) and the experimental administration of interleukin-12 (IL-12), as well as tumor necrosis factor (TNF)-alpha and other biological agents. High dose IFN alfa-2b (INTRON® A) has demonstrated an improvement in survival for Stage IIB- III patients in the adjuvant (postoperative) setting. High dose IL-2 (Proleukin®) has been approved by the FDA for treatment of patients with metastatic (Stage IV) melanoma on the basis of Phase II trials showing prolonged survival in a subset of patients (16%) who demonstrate tumor regression with this agent; however, the side effects of systemically administered IL-2 and IFN alfa-2b can be severe and limiting. Ipilimumab, an anti-CTLA-4 monoclonal antibody used to overcome or reverse T cell suppression and thereby potentiate an anti-tumor T cell response, was approved by the FDA for treatment of unresectable Stage III and IV melanoma on the basis of a Phase III trial which demonstrated an improvement in median overall survival. In that study, there were 14 deaths related to the study drugs and 7 were associated with immune related adverse events.³ Other immunotherapies for the treatment of melanoma are also in various stages of development, including immune checkpoint inhibitors, and OncoVEX^{GM-CSF}, an oncolytic herpes simplex virus encoding GM-CSF.

The results from these studies demonstrate that other, safer and still effective immunotherapies are greatly needed for patients with advanced melanoma.

5.2 BACKGROUND INFORMATION FOR GENE THERAPY COMPONENTS

[figure not shown]
[REDACTED]

The Phase I/II study proposed in this protocol (ATI001-101) will examine the safety, anti-tumor activity, and immunological effects of intratumoral injections of INXN-2001 in combination with orally administered INXN-1001 as a potential anticancer therapy in subjects with advanced melanoma.

5.2.2 INXN-2001 (Ad-RTS-hIL-12)

INXN-2001 (Ad-RTS-hIL-12) is comprised of the replication-incompetent adenovirus vector with human interleukin-12 (hIL-12) as the [redacted] regulated transgene (Figure 2), as described by Anderson *et al.*⁶ Cells transduced with INXN-2001 will produce hIL-12 protein if transcription has been activated in the presence of the small molecule ligand, INXN-1001. Because the level of transgene expression (ie, protein production) is ligand-concentration dependent, hIL-12 production can be modulated by the dose and frequency of oral INXN-1001 administration. Therefore, potential IL-12-related adverse events may be relieved by withdrawal of INXN-1001 administration, if necessary.

5.2.3 INXN-1001 (ACTIVATOR LIGAND)

INXN-1001 is an orally active small molecule [REDACTED]

[REDACTED]

[REDACTED]

[REDACTED]

5.3 BACKGROUND AND RATIONALE FOR TREATMENT STRATEGY

5.3.1 IL-12 Immunotherapy

Cytokine-mediated, anti-tumor effects have been studied in a number of tumor model settings as well as clinical trials. The short half-lives of most cytokines, coupled with the cost and difficulties of manufacturing, delivery, and severe side effects associated with high systemic doses, have limited their use as a therapy. Although small amounts of endogenously synthesized cytokines may circulate systemically, cytokines are generally produced and act at precise sites in very high local concentrations. These facts have made attractive the local delivery of cytokines directly into tumors. This might be accomplished by gene therapy to enhance the local anti-tumor response and locally reverse tumor-induced tolerance. Indeed, local cytokine delivery to tumors can induce a number of anti-tumor responses that include: 1) direct suppression of tumor cell proliferation, 2) induction of apoptosis, 3) anti-angiogenesis, and 4) enhancement of local anti-tumor immune response. This enhancement of local anti-tumor response can be further characterized by

cytokine-mediated activation of natural killer (NK) cells and cytotoxic T lymphocytes (CTLs), as well as the modulation of major histocompatibility molecule expression.⁸

Interleukin (IL)-12 is a potent immunostimulatory cytokine which has promise as a cancer therapeutic agent that remains to be realized in the clinic. IL-12 activates and recruits dendritic cells (DC) which in turn, facilitate the cross-priming of tumor antigen-specific T cells. IL-12 functions as a key mediator for the generation of TH1 CD4+ effector T cells, activation of natural killer (NK) and CD8⁺ T cell cytotoxic activities, and the production of IFN- γ and TNF- α .⁹⁻¹² IL-12 also has anti-angiogenic activity. Administration of IL-12 has been shown to significantly reduce or eradicate tumor growth and to enhance survival in numerous animal models of cancer.¹³⁻¹⁷ Significant results observed in these tumor models after IL-12 treatment have been correlated with the ability of IL-12 to stimulate anti-tumor immunity and suggests that this cytokine may be applied as a novel immunotherapy in human cancers.

Clinical trials have been performed to assess the safety and efficacy of administering recombinant IL-12 protein to subjects with cancer, including, but not limited to, melanoma, renal cell carcinoma, colorectal, cervical, ovarian, and lung metastases. IL-12 protein was delivered via intravenous (IV), intraperitoneal (IP), or subcutaneous (SC) administration.¹⁸⁻²⁷ Administration of IL-12 systemically resulted in induction of immune responses in some subjects but there was limited clinical improvement and severe toxicity. In a Phase II trial evaluating repeated iv administration of rhIL-12 in subjects with renal cell carcinoma, 12/17 subjects were hospitalized and two died due to hypovolemic shock. The study was halted as most subjects experienced SAEs during the first cycle of treatment. There was a high frequency of Grade 3 and 4 AEs, with 65% of subjects showing leukopenia and 47% showing hyperbilirubinemia and elevated AST.²⁷ Based on reports to date, strategies for the local delivery of IL-12 through gene therapies may represent a safer and acceptable treatment approach in cancer patients.

[REDACTED]

[REDACTED]

[REDACTED]

[REDACTED]

